### *Duration of study*

The data collection will last for 6 months – from 1/7/17 to 1/12/17

### *Data analysis*

For each instruction, the recorded time for twenty five repetitions will be converted to a rate of repetitions/minute. The time taken to perform the twenty five repetitions under instruction will be compared with baseline to calculate an percentage increase in rate of repetitions.

A repeated measures ANOVA will be used to ascertain the effect of the different types of instructions on the percentage increase in rate of repetitions.

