### *Data collection:*

The Stroke survivor will do their usual exercises in Bankstown-Lidcombe rehabilitation gym. The researcher will observe the participant perform twenty five repetitions of one exercise under no instruction. This will be timed to form a baseline. Following this, the researcher will use one of three different types of instructions to direct their practice of the same exercise. The participant will receive a different instruction each day across three days. The order of these three types of instructions will be randomised giving six possible orders. Each patient will be randomly assigned to one of the six orders..

The types of instructions that will be used will be (using standing up as an example); an instruction with an endpoint such as “can you stand up and sit down 25 times”, an instruction with a time component such as “can you stand up and sit down 25 times as fast as you can”, and an instruction with motivation such as “can you stand up and sit down 25 times as fast as you can, aim for your personal best!!”.

The order of the instructions will be randomised across the three days allowing for each of the three instructions to be used. The time taken to perform the twenty five repetitions under each instruction will be recorded.

A new baseline will be measured each day to account for recovery over the three days. Data will be collected at a similar time each day to reduce the risk of fatigue affecting rate of repetitions.

*Source of participants:*

The participants for this study will be Stroke survivors admitted to Bankstown Stroke unit who meet the inclusion criteria.

*Sample size*

There are three different instructions that are being tested. The order of instructions will be randomized. There are six different orders that the instruction can be presented. Therefore, the participants will be randomised to one of six groups. Six groups of three participants will be recruited to account for any affect that the order of instructions has on the rate that the repetitions are performed. Therefore, a total of approximately eighteen participants will be recruited for this study.

*Inclusion criteria:*

- Stroke is diagnosed by clinical presentation, CT or MRI scan results
- All Stroke types are eligible (haemorrhagic or ischaemic)
- The admission period is likely to be more than one week
- The participant can perform 50 repetitions of either stand ups, tilt table or sit and reach without physical assistance

*Exclusion criteria:*

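### Dividing by a single same-day baseline, instead of adjusting for it, costs precision by an amount the protocol does not let one fix; adjusting log rate for that baseline is a cheap improvement

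*Protocol*

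**What the plan says.** Protocol section 5, Data analysis, converts each recorded time to repetitions per minute. It then states that the time under instruction "will be compared with baseline to calculate an percentage increase in rate of repetitions". The test follows: "A repeated measures ANOVA will be used to ascertain the effect of the different types of instructions", applied to that percentage. Neither a log scale nor a baseline covariate is mentioned.

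The denominator is defined under Data collection. The participant is observed to "perform twenty five repetitions of one exercise under no instruction", and this is timed; no replicate is described. It is repeated daily: "A new baseline will be measured each day to account for recovery over the three days".

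Under Sample size, the number of participants comes from balance over the orders alone: "There are six different orders that the instruction can be presented", "Six groups of three participants will be recruited", and so "a total of approximately eighteen participants will be recruited for this study". The inclusion criteria allow different exercises, "either stand ups, tilt table or sit and reach without physical assistance", so raw rates will differ in level between participants.

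**The concern.** The outcome is a ratio of two timed sets from the same session. On the log scale this subtracts log baseline with a coefficient of exactly 1, whatever the data say about how well baseline predicts the instructed rate. Any chance error in that one set passes undiminished into the percentage, and this happens separately on each of the three days.

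The crossover already removes stable differences between people. The daily baseline is therefore only needed to remove day-to-day variation, including recovery. A regression coefficient does this with the weight the data support; a forced coefficient of 1 usually over-corrects.

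The percentage scale is also asymmetric: equal proportional gains and losses do not give percentages of equal size.

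What is at stake is the precision of a small trial whose size was set without a power calculation, so no margin of precision has been shown.

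**Working it through.** **Inputs.** From the protocol: 6 orders × 3 participants = 18, which reproduces the stated total; one baseline and one instructed set per day; three days. Not in the protocol, and therefore assumed:
- r, the same-day correlation of log baseline and log instructed rate within participants, after stable differences between people are removed;
- k, the baseline SD divided by the instructed SD (within participants, log scale).

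**Step 1: variance.** Let s² be the within-participant variance of log instructed rate.
- Log ratio (approximately the percentage): s²(1 + k² − 2kr).
- Adjusted for log baseline: s²(1 − r²).
- Ratio of the two: 1 + (k − r)²/(1 − r²). This is never below 1, and equals 1 only when k = r.
- With k = 1 it becomes 2/(1 + r), so 18 participants are worth 18(1 + r)/2.

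| r (assumed) | Variance ratio, k = 1 | 18 are worth | Lost | Needed to match 18 adjusted |
|---|---|---|---|---|
| 0.2 | 1.67 | 10.8 | 7.2 | 30 |
| 0.3 | 1.54 | 11.7 | 6.3 | 28 |
| 0.5 | 1.33 | 13.5 | 4.5 | 24 |
| 0.7 | 1.18 | 15.3 | 2.7 | 22 |
| 0.8 | 1.11 | 16.2 | 1.8 | 20 |
| 0.9 | 1.05 | 17.1 | 0.9 | 19 |

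**Step 2: unequal variances.**
- k = 0.7: 1.07/0.91 = 1.18 at r = 0.3; 0.79/0.75 = 1.05 at r = 0.5; 0.51/0.51 = 1.00 at r = 0.7. The loss is below the equal-variance figure as long as 1.49 − 1.4r < 2(1 − r), that is r < 0.85.
- k = 1.4: 2.12/0.91 = 2.33; 1.56/0.75 = 2.08; 1.00/0.51 = 1.96 at the same three values.

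**Step 3: simulation with the slope estimated.** 18 participants, three periods, 1,500 trials per setting, k = 1, within-participant log SD 0.1 and 0.2. The largest difference between instructions was set to 1 residual SD of the adjusted model. Variance ratio is percentage against adjusted log rate, as squared coefficients of variation.

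| r | Simulated variance ratio | Power, percentage | Power, adjusted log rate |
|---|---|---|---|
| 0.2 | 1.61–1.66 | 0.49–0.51 | 0.71–0.73 |
| 0.5 | 1.29–1.35 | 0.57 | 0.71 |
| 0.8 | 1.08 | 0.67–0.69 | 0.72–0.73 |
| 0.9 | 1.02–1.03 | 0.72–0.73 | 0.72–0.74 |

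The simulated ratios lie close to the formula, so estimating the slope costs little. Power for the unadjusted log ratio was within about 1 point of that for the percentage. Nearly all the gain therefore comes from adjusting instead of dividing, and little from the log.

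**Step 4: scale.** A rate going from 10 to 12.5 is +25%; the reverse is −20%. If the log ratio is normal with SD 0.2, the percentage has skewness 0.61 and mean 100(exp(0.02) − 1) = +2.0% with no true effect. With SD 0.4 these are 1.32 and +8.3%.

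**Step 5: one bad baseline.** If one baseline rate is 30% too low and there is no true gain, the value rises by 100(1/0.7 − 1) = 42.9 points, or 42.9/18 = 2.4 points in a mean of 18. On the log-ratio scale the shift is 35.7/18 = 2.0 log points.

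**The case against.** The best defence is that the planned analysis is valid and has a purpose. The daily baseline handles recovery, a percentage puts the three exercises on one relative scale, and it expresses gain over no instruction, which is close to the aim in section 7 of learning whether instructions affect repetitions. All of that stands. It is why the percentage should be kept as a reported measure.

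The size of the loss is also not established by the document, which gives no SD, effect size or correlation. In a second simulation, with effects of 0, 12 and 15 log points, SD 15 log points and a day term, power for the percentage against the adjusted analysis was 61% against 80% at r = 0.3, 76% against 88% at r = 0.5 and 94% against 97% at r = 0.7, but 99.1% against 99.4% at r = 0.8. Part of that convergence is a ceiling, because a fixed effect becomes easy to detect as r rises. Step 3 avoids the ceiling and still shows little difference at r = 0.9.

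Four stronger readings are tempting, and the documents do not support them:
- **That several participants' worth of precision is certainly lost.** This depends on r and k, and neither is given. Because r is what remains after stable differences are removed, it is probably lower than the overall correlation. That makes a material loss plausible, not shown.
- **That one slow baseline could dominate a mean of 18.** Step 5 gives a shift of about 2.4 points.
- **That the comparison of instructions is biased.** Order is randomised, and the upward shift in Step 4 applies to all three instructions and largely cancels between them.
- **That the percentage is ambiguous between time and rate.** For 60 s falling to 45 s, these would be 25% and 33%. The wording sets time beside rate loosely, but Data analysis first converts times to a rate and then names an increase in rate, so the 33% reading is plain.

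**Conclusion.** The point holds as a matter of efficiency, not validity. The protocol itself fixes both the outcome and the test, so this is not a detail left to a later plan. The outcome carries the full error of a single baseline set and sits on a mildly skewed scale, and baseline adjustment is in expectation at least as precise.

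Under equal variances the loss runs from about 7 of 18 participants at r = 0.2 to about 1 at r = 0.9. It is larger if the baseline is the more variable measure. It is generally smaller if the baseline is the less variable one, and nil at r = 0.7 when the baseline SD is 0.7 of the instructed SD. Both r and the variance ratio are assumptions. The change is worth making because it costs almost nothing, not because the planned analysis would mislead.

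**What to change.** In section 5, Data analysis, make the primary outcome log(repetitions/minute) under instruction. Fit participant (as a fixed effect), day and instruction, with same-day log baseline rate as a covariate. Fixed participant effects keep the baseline coefficient a within-person one. Back-transform the differences between instructions to percentage differences in rate with 95% CIs. Same-day baseline still accounts for recovery, and the results stay relative across the three exercises.

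Still report the percentage increase over baseline for each instruction, defined as 100 × (baseline time / instructed time − 1), with a CI, as the secondary measure of gain over no instruction.

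Cost: a wording change, with every value already collected. The covariate uses one degree of freedom. With 54 observations, participant and instruction alone leave 54 − 18 − 2 = 34 for error; a day term, if not already intended, takes 2 and the covariate 1, leaving 31. The other downside is that the primary contrast is between instructions, with gain over no instruction moved to the secondary measure.

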## **5. RESEARCH PLAN / STUDY DESIGN**

### *Type of study:*

This will be a randomized cross-over study.

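### Add day as a factor to the repeated measures ANOVA: it uses the order structure the trial already randomises by, and without it any day effect on the gain widens the intervals

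*Protocol*

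**What the plan says.** Section 5 of the Protocol describes a cross-over design in which "The participant will receive a different instruction each day across three days". All orders are used: "The order of these three types of instructions will be randomised giving six possible orders".

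Under Sample size, the number of participants rests on order alone: "Six groups of three participants will be recruited to account for any affect that the order of instructions has on the rate". From this it follows that "a total of approximately eighteen participants will be recruited for this study". Under Data collection the allocation is described only as "Each patient will be randomly assigned to one of the six orders", with no mechanism such as a list or blocks.

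Day-to-day change is addressed through the outcome: "A new baseline will be measured each day to account for recovery over the three days". Under Data analysis, the time for 25 repetitions becomes a rate and then a percentage increase over baseline. The model sentence is "A repeated measures ANOVA will be used to ascertain the effect of the different types of instructions" on that percentage increase. Instruction is the only effect it names. Day, period and order do not appear in it.

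**The concern.** The trial randomises by order and sizes itself by order, but the stated analysis does not use that structure. In a three-period cross-over, day is a known and recorded source of variation, and leaving it out sends any day effect into the residual.

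The same-day baseline deals with part of this. It does not deal with changes in the gain itself: growing familiarity with being timed, fading novelty, or an uninstructed baseline that is already faster on day 2 because the participant was asked for speed on day 1. Two of the three instructions ask for speed, so the last of these is plausible.

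At stake is precision. With about 18 participants and no power calculation, there is little of it to spare.

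**Working it through.** **1. The plan's own figure.** Three instructions give 3! = 6 orders, and 6 × 3 = 18 participants. This matches the Protocol. It is a count, not a power calculation: no significance level, effect size or SD is given.

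**2. What the daily baseline removes.** Percentage gain = 100 × (instructed rate ÷ baseline rate − 1). If a day multiplies both rates by the same factor, the factor cancels, so proportional recovery drops out. A day effect on the ratio itself does not cancel.

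**3. Degrees of freedom.** There are 18 × 3 = 54 gains, with 17 df between participants and 2 for instruction.
- Without day: 54 − 1 − 17 − 2 = 34 error df.
- With day: 34 − 2 = 32.

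**4. Error variance with three participants per order.** Let the gain shift by d within-person SDs per day, so the day effects are (−d, 0, +d). Each instruction then falls on each day six times, so day is orthogonal to instruction and its whole sum of squares, 18 × 2d² = 36d², goes into the residual:

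expected error variance ÷ true variance = 1 + 36d²/34

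- d = 0.25: 1 + 2.25/34 = 1.07
- d = 0.5: 1 + 9/34 = 1.26
- d = 1: 1 + 36/34 = 2.06

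The 95% interval half-width, relative to the model with day, is the square root of this ratio times 0.998 (the ratio of the t quantiles on 34 and 32 df).

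**5. Level and power.** These come from 20,000 simulated trials per scenario. Assumptions not in the Protocol: a 5% test, normal errors, the values of d, and instruction effects of 0, 0.5 and 1 SD for power.

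| d (SD per day) | Error variance × | Half-width ratio | Actual level, without / with day | Power, without / with day |
|---|---|---|---|---|
| 0 | 1.00 | 1.00 | 4.9% / 4.8% | 73% / 73% |
| 0.25 | 1.07 | 1.03 | 4.4% / 5.2% | 70% / 73% |
| 0.5 | 1.26 | 1.12 | 2.2% / 4.9% | 62% / 73% |
| 1 | 2.06 | 1.43 | 0.3% / 5.3% | 32% / 73% |

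Both models estimate the instruction contrasts without bias in every row.

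**6. If the orders end up unequal.** The same simulation was run with each participant's order drawn independently. The standard error reported without day is then close to the real spread of the estimate: 0.37 against 0.38 SD at d = 0.5, and 0.47 against 0.48 at d = 1. The actual level stays near 5% (5.3% and 5.6%). What is lost is precision. Power without and with day is 62% against 70% at d = 0.5, and 42% against 70% at d = 1. With no day effect, the day term costs a little: 73% without it, 70% with it.

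**The case against.** **The model sentence may simply be brief.** It names a family of methods and the effect of interest, and does not say that day is left out. A statistical analysis plan may list day as a term. That is fair, and if it does, the analysis half of this point is already met. The suggestion remains useful because the Protocol names its analysis and justifies its design by order, yet does not connect the two.

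**Counterbalancing already accounts for order.** A reader might infer that the order control is lost in the analysis. The document does not support that. Six orders of three is a design device, and it keeps the instruction contrasts free of day effects whether or not day is modelled. Only precision can suffer.

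**A reader might infer that the error bars are wrong in general, or that uneven orders bias the result.** Neither follows. The harm needs a day effect that survives the same-day baseline, and the Protocol reports none. With balanced orders the error is on the conservative side. With independently drawn orders the standard errors are about right, and chance imbalance adds random error with expectation zero, not systematic bias.

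**The Protocol fixes three per order.** This also stands. Independent draws would give exactly three in every order with probability 18!/(3!⁶ × 6¹⁸) = 0.14%, so the stated groups of three imply some restricted allocation. What is missing is only the mechanism that delivers them.

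**Conclusion.** The point holds as an efficiency improvement. The stated ANOVA names instruction only, so any day effect on the percentage gain goes into the error term. With three participants per order there is no bias and no excess of false positives; intervals are too wide and the test is conservative.

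The loss cannot be fixed from the document. Over assumed shifts of 0 to 1 within-person SD per day, it runs from nothing to intervals 43% wider. At 0.25 SD per day it is small. The range assumes a linear shift common to all participants and normal errors. A day term removes only the part of practice or carry-over that is shared by everyone on a given day. It does not remove carry-over that depends on which instruction came the day before.

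This is a free improvement, not a must-fix error.

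**What to change.** **Data analysis:** state that the percentage increase will be analysed with participant, day (1, 2, 3) and instruction as factors, and that the instruction contrasts will be reported with confidence intervals.

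**Data collection:** state that orders are drawn from one shuffled list of 18 places holding each of the six orders exactly three times, so that the stated groups of three are delivered.

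**Cost:** two changes of wording, a prepared allocation list and 2 of 34 error degrees of freedom. No new data are needed. If there is no day effect and the orders are balanced, almost nothing is lost.

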## **6. ETHICAL CONSIDERATIONS**

### *Recruitment and selection of participants:*

The participants for this study will be Stroke survivors admitted to the Stroke unit at Bankstown Lidcombe Hospital who meet the inclusion criteria.

### *Informed consent:*

[name] will meet with patients that meet inclusion criteria and their family if appropriate and explain the research project. Potential participants and/or carers will be individually given a participant information letter. Contact details to discuss this further will be included as well as the opportunity to discuss the project at the time of being given the participant information letter. Patients will be told that [name] will come back in two days to allow time to read the information letter, discuss the information with family members and decide whether they are interested in participating. Questions will be encouraged at both meetings.

Consent will be recorded on consent forms.

Participants who are able to give their consent will also be given the choice of what they would like to happen should they lose the capacity to consent during the research data collection period. This shall be recorded in the consent form.

Mini-Mental State Examination (MMSE) score in the medical record will be used to determine the cognitive capacity of the potential participant to consent. A MMSE score less than 21 suggests that the individual is unable to provide consent themselves

and their Person Responsible will be asked to decided if they will be included in the study or not. A MMSE great than 21 signifies that an individual is capable to providing their own consent.

*Confidentiality and privacy:*

Upon recruitment, the participant will be de-identified and given a unique identification number. Data will be stored on an Excel spreadsheet on a password protected computer in a locked office. Only the research team will have access to this data.

*Data storage and record retention:*

The data will be collected on paper in the Bankstown-Lidcombe rehabilitation gym and then transferred on to an Excel spreadsheet on a password protected computer in the Physiotherapy Rehabilitation office. The paper will be shredded after it is transferred onto the computer.

The Physiotherapy Rehabilitation office is a locked office and all the computers are password protected. The data analysis will be done on a computer in this office. The data will be stored on a computer in this office for five years. At the conclusion of five years the data will erased from the computer by [name].

*Risks:*

The risks in this intervention are no greater than the usual demands of exercise. To manage the risks of exercise, there will always be one researcher and one other physiotherapist present when the participants are performing their exercise. They will be closely observed to ensure they are not experiencing discomfort whilst exercising. The participant will also be informed that they should stop exercising if they experience pain, or discomfort.

Furthermore, participants will be excluded from the study if they are medically unstable, as determined by the medical team.

The instructions delivered to the participants are not different to what would commonly be used in clinical practice. Therefore, the participants are very unlikely to exert themselves beyond what they would in normal rehabilitation.

**Vulnerable group**

Stroke survivors may fall into the vulnerable category, as defined as ‘people with a cognitive impairment, an intellectual disability or mental illness’ (10). Individuals with a cognitive impairment will still be included in the study. Consent from these individuals will be sought from that person if they have the capacity to consent or from their Person Responsible. The ability to consent will be determined by the potential participants Mini-Mental State Examination results. If their score is 21 or higher, the individual has the capacity to consent for themselves. If their score is

below 21, it is deemed that they do not have the capacity to consent and their Person Responsible will provide consent on the participants behalf.

## **7. OUTCOMES AND SIGNIFICANCE**

Evidence suggests that large amounts of repetitious practice are necessary for functional improvement after Stroke. However, this is not being achieved in rehabilitation sessions in Stroke units across the globe. The potential benefit of this study is to establish if instructions have an affect on the number of repetitions performed in rehabilitation. This information will assist therapists to deliver the most suitable instruction to Stroke survivors to ensure that the fastest rate of repetitions are being performed during rehabilitation. This may allow for greater repetitions to be performed over a session.

This study will contribute to the research on intensity of practice in Stroke rehabilitation and provide insight into the affect of instructions, an area where research is currently very limited.

Participants will not receive any direct benefit as a result of their participation, other than establishing which instruction results in the fastest rate of repetitions. Family members and therapists can use this information for the duration of their Stroke rehabilitation.

